#### 7.1. Prior and Concomitant Medications

If a medication ended before IM injection, then it will be categorized as prior medication; if a medication started or kept using on or after IM injection then it will be categorized as concomitant medication. All medications will be mapped to preferred terms according to the World Health Organization (WHO) drug dictionary September 2020 or later. The number and percentage of all subjects in the SAS population having prior medications or concomitant medications will be tabulated by Anatomical Therapeutic Chemical Code Level 3 (ATC3) classification system and WHO drug preferred term (PT). At each level of summarization, a subject is counted only once if she/he reported one or more medication. All prior and concomitant medications will be presented in listings.

### 7.2. Concomitant Procedures or Non-Drug Therapy

All concomitant procedures or non-drug therapy data will be presented in listings.

### 7.3. Study Treatments

Exposure to study treatments will be summarized for all subjects in the SAS population. Number and percentage of subjects who received vaccine administration and the volume

Medicago USA Page 30 of 55

administered will be summarized using descriptive statistics. All vaccine administration information recorded in eCRF will be presented in a listing.

# 7.4. Randomization

The randomization number and relevant information will be presented in a listing.

Medicago USA Page 31 of 55

# 8. Immunogenicity Analysis

All the primary and secondary immunogenicity evaluations will be analyzed by treatment group and strain based on the PP populations (the one belonging to the particular visit) and will include each treatment group as a whole. Sensitivity analyses will be performed using the ITT population and all collected data will be listed. Reverse Cumulative Distribution Curves (RCDC) will be presented for each post-baseline visit, as follows: homologous & heterologous strains measured by HI, based on PP sets; homologous strains measured by HI, based on PP sets.

# 8.1. Primary Immunogenicity Analysis

The primary immunogenicity analysis endpoint is to evaluate the HI antibody response induced by adjuvanted and unadjuvanted QVLP and Fluzone HD Quad against the homologous influenza strains on Day 28, compared to Day 0 values, analyzed as follows:

- GMT at Day 0 and Day 28;
- SC rate at Day 28: the proportion of subjects in a given treatment group with either a ≥ 4-fold increase in reciprocal HI titers between Day 0 and Day 28 or a rise of undetectable HI titer (i.e., < 10) pre-vaccination (Day 0) to an HI titer of ≥ 40 on Day 28:
- SP rate at Day 28: the proportion of subjects in a given treatment group attaining a reciprocal HI titer of ≥ 40 on Day 28 (the percentage of vaccine recipients with a serum HI titer of at least 1:40 following vaccination);
- GMFR (Day 28/Day 0): the geometric mean of the ratio of GMTs (Day 28/Day 0).

For the H1 and H3 analysis, results from the assay using VLP reagents will be used. Any antibody titer that is below the LLOQ of assay will be imputed with a value equal to half of the LLOQ of assay of the antigen specific antibody titer.

GMT will be calculated as anti-logarithm of ( $\sum$ (log-transformed titer)/number of subjects with titer information). The 95% CI for GMT will be calculated as the anti-log transformation of upper and lower limits for a 2-sided CI of the mean of the log-transformed titers. The log-transformed GMT will be compared among treatment groups by using the analysis of variance (ANOVA) model on log-transformed titer values and the Tukey's test will also be performed for the pairwise comparisons between treatment groups within the frame of the same model.

The point estimates and the corresponding two-sided 95 % Clopper-Pearson CI [Clopper, 1934] for subjects achieving SC and SP will be calculated and compared among treatment groups using Fisher's exact test.

GMFR will be calculated as anti-logarithm of  $\sum$  [log-transformed titer ratio of Yi/Bi)/number of subjects with titer information], where Yi is the post-vaccination titer and Bi is the pre-vaccination (baseline) titer for subject i. The 95% CI for GMFR will be calculated as the anti-log transformation of upper and lower limits for a 2-sided CI of the mean of the log-transformed titers fold rise from pre-vaccination. The log-transformed

Medicago USA Page **32** of **55** 

GMFRs will be compared among treatment groups by using analysis of covariance (ANCOVA) with treatment group as main effect and baseline as covariate on log-transformed titer values fold rise from pre-vaccination. Tukey's test will be performed for pairwise comparisons between treatment groups within the frame of the same model.

SAS code is presented in Appendix 13.3.

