10.3.2.1 Primary Endpoint

- HI antibody response induced by adjuvanted and unadjuvanted QVLP and Fluzone HD Quad against the homologous influenza strains on Day 28, compared to Day 0 values, will be analyzed as follows:
 - GMTs of HI antibody on Days 0 and 28;
 - SC rate: the proportion of subjects in a given treatment group with either a ≥ 4-fold increase in reciprocal HI titers between Day 0 and Day 28 or a rise of undetectable HI titer (i.e. < 10) pre-vaccination (Day 0) to an HI titer of ≥ 40 on Day 28;
 - SP rate: the proportion of subjects in a given treatment group attaining a reciprocal HI titer of ≥ 40 on Day 28 (the percentage of vaccine recipients with a serum HI titer of at least 1:40 following vaccination);
 - GMFR: the geometric mean of the ratio of GMTs (Day 28/Day 0).

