10.3.2.2 Secondary Endpoints

- MN antibody response induced by adjuvanted and unadjuvanted QVLP and Fluzone HD Quad against the homologous influenza strains on Day 28, compared to Day 0 values, will be analyzed as follows:
 - GMTs of MN antibody on Days 0 and 28;
 - SC rate: the proportion of subjects in a given treatment group with either a ≥ 4-fold increase in reciprocal MN titers between Day 0 and Day 28 or a rise of undetectable MN titer (i.e. 7.1) pre-vaccination (Day 0) to an MN titer of ≥ 28.3 at Day 28 post-vaccination;
 - GMFR: the geometric mean of the ratio of GMTs (Day 28/Day 0).

- HI antibody response induced by adjuvanted and unadjuvanted QVLP and Fluzone HD
 Quad against the heterologous influenza strains on Day 28, compared to Day 0 values. HI
 antibody titers will be analyzed as follows:
 - GMTs of HI antibody on Days 0 and 28;
 - SC rate: the proportion of subjects in a given treatment group with either a ≥ 4-fold increase in reciprocal HI titers between Day 0 and Day 28 or a rise of undetectable HI titer (i.e. < 10) pre-vaccination (Day 0) to an HI titer of ≥ 40 on Day 28;
 - SP rate: the proportion of subjects in a given treatment group attaining a reciprocal HI titer of ≥ 40 on Day 28 (the percentage of vaccine recipients with a serum HI titer of at least 1:40 following vaccination);
 - GMFR: the geometric mean of the ratio of GMTs (Day 28/Day 0).
- HI antibody response (against homologous and heterologous influenza strains) and MN antibody response (against homologous influenza strains) induced by adjuvanted and unadjuvanted QVLP and Fluzone HD Quad on Day 28, compared to Day 0 values, stratified by prior influenza vaccination status, if >25% of the enrolled subjects have received a standard influenza vaccine during the 12 months prior to study vaccination;
- Durability of antibody responses 6 months post-vaccination, as determined by HI antibody responses induced by adjuvanted and unadjuvanted QVLP and Fluzone HD Quad against the homologous influenza strains on Day 182, compared to Day 0 values.
 - HI antibody titers will be analyzed as follows:
 - GMTs of HI antibody on Day 182;
 - SC rate: the proportion of subjects in a given treatment group with either a ≥ 4-fold increase in reciprocal HI titers between Day 0 and Day 182 or a rise of undetectable HI titer (i.e. < 10) pre-vaccination (Day 0) to an HI titer of ≥ 40 on Day 182;

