 - SP rate: the proportion of subjects in a given treatment group attaining a reciprocal HI titer of ≥ 40 on Day 182 (the percentage of vaccine recipients with a serum HI titer of at least 1:40 following vaccination);
 - GMFR: the geometric mean of the ratio of GMTs (Day 182/Day 0).
- Durability of antibody responses 12 months post-vaccination, as determined by HI antibody responses induced by adjuvanted and unadjuvanted QVLP and Fluzone HD Quad against the homologous influenza strains on Day 365, compared to Day 0 values.
 - HI antibody titers will be analyzed as follows:
 - GMTs of HI antibody on Day 365;
 - SC rate: the proportion of subjects in a given treatment group with either a ≥ 4-fold increase in reciprocal HI titers between Day 0 and Day 365 or a rise of undetectable HI titer (i.e. < 10) pre-vaccination (Day 0) to an HI titer of ≥ 40 on Day 365;
 - SP rate: the proportion of subjects in a given treatment group attaining a reciprocal HI titer of ≥ 40 on Day 365 (the percentage of vaccine recipients with a serum HI titer of at least 1:40 following vaccination);

• GMFR: the geometric mean of the ratio of GMTs (Day 365/Day 0);

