#### 10. Interim Analysis

Interim analyses will be performed (i) after Day 28 HI data available as of the Feb. 12, 2021 data transfer, (ii) after the last subject has completed Day 28 assessments and (iii) after the last subject has completed Day 182 assessments.

The first interim analysis based on Day 28 HI data available as of the Feb. 12, 2021 data transfer will inform a business decision to confirm the vaccine formulation for a Phase 2/3 study for AdjQVLP and will include immunogenicity analyses for HI Antibody Response against Homologous Influenza Strains (GMT, GMFR and SC and SP rate analyses).

The second interim analysis will include all tables.

The third interim analyses at Day 182 will be a full interim analysis with all tables/listings/figures planned for the final analysis.

The results of the interim analyses will be confidential and strictly limited to the authorized staff members and will allow discussions of the clinical data to inform study design decisions of the subsequent study, without having to wait until after the end of the follow-up period for study completion. No adjustments to the final analyses as a result of these interim analyses were therefore deemed necessary.

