#### 11. Changes in the Planned Analysis

• The second interim analysis at Day 28 with 120 subjects (30%) described in Section 10 is added as an ad-hoc analysis upon agreement with FDA. The purpose is to

Medicago USA

- mitigate the risk of administration of an investigational vaccine during influenza season to an elderly population.
- Initially, Fisher's exact test or Chi Square test were planned to compare number of subjects achieving SC and SP. However, only Fisher's exact test will be used.
- An interim analysis based on Day 28 HI data available as of the Feb. 12, 2021 data transfer was added in Section 10 to inform a business decision to confirm the vaccine formulation for a Phase 2/3 study for AdjQVLP.
- The interim analysis at Day 28 with 120 subjects (30%) is removed after confirmation from CBER. Full Day 28 interim analysis will be shared with FDA instead.
- Full Day 28 interim analysis will include all tables instead of demographic tables, tables relating to all immunogenicity analyses, AE overview, immediate solicited AEs, solicited AEs up to Day 7, related unsolicited AE by intensity, SAEs and AESIs.

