#### Analysis of SC/SP

• 95% CI

PROC FREQ data=tab;

BY STRAIN TRT;

TABLE var / binomial (exact); \*\* where var=Subject achieving SC or SP

RUN:

• Fisher's Exact Test:

PROC FREQ data=tab;

BY STRAIN;

TABLE var\*TRT/ fisher; \*\* where var=Subject achieving SC or SP

RUN:

Note: The MN assay will be performed on Day 0 and Day 28 only, and not on Day 182 and Day 365.

Confidential

Medicago USA Page 48 of 55

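### As written, HI seroconversion can be met by a rise from <10 to only 20 if the assay's LLOQ is 10, because the 4-fold limb has no baseline condition and half-LLOQ imputation has no seroconversion exception

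*SAP*

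**What the plan says.** SAP 8.1 joins two limbs by either/or. A subject seroconverts with at least a "4-fold increase in reciprocal HI titers between Day 0 and Day 28 or a rise of undetectable HI titer (i.e., < 10") to a titer of 40 or more. Protocol 10.3.2.1 has the same second limb: "or a rise of undetectable HI titer (i.e. < 10) pre-vaccination (Day 0) to an HI titer of ≥ 40 on Day 28". Protocol 10.3.2.2 repeats the rule for heterologous strains at Day 28 and for the durability endpoints ("pre-vaccination (Day 0) to an HI titer of ≥ 40 on Day 182" and "pre-vaccination (Day 0) to an HI titer of ≥ 40 on Day 365"). SAP 8.2 carries the primary method over to the secondary HI endpoints. In none of these places does the 4-fold limb require a measurable baseline.

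SAP 8.1 also says that any antibody titer below the LLOQ "will be imputed with a value equal to half of the LLOQ of assay". The sentence covers all titers and does not set SC aside. Neither document gives a value for the HI LLOQ.

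The code in SAP 13.3 does not settle the derivation. It starts from a finished flag: "where var=Subject achieving SC or SP".

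**The concern.** A separate ≥40 threshold for undetectable baselines makes sense only if such subjects are meant to reach 40. Read literally, the imputation rule lets them qualify through the 4-fold limb at a lower titer. Two careful programmers could therefore derive different SC rates from the same data.

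SC rate is one of the four parameters of the primary immunogenicity endpoint. The same rule feeds the heterologous, Day 182, Day 365 and prior-vaccination analyses. SC is also in the interim analyses: the first "will include immunogenicity analyses for HI Antibody Response against Homologous Influenza Strains (GMT, GMFR and SC and SP rate analyses").

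**Working it through.** The documents state no SC rate, power or sample size calculation to reproduce, so the check applies the written rule directly.

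**Inputs.** The two limbs and the half-LLOQ rule are from SAP 8.1. The arm size of 40 is from SAP 4.1. The HI LLOQ is an assumption: 10 is the value suggested by the undetectable cut-off, and 4 to 20 was examined.

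**Step 1: lowest qualifying titer.** A baseline below the LLOQ is set to LLOQ/2. The 4-fold limb is then met at 4 × LLOQ/2 = 2 × LLOQ.

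| Assumed LLOQ | Imputed baseline | Lowest titer meeting 4-fold limb | Titers counted as SC although below 40 |
|---|---|---|---|
| 4 | 2 | 8 | 8 to <40 |
| 5 | 2.5 | 10 | 10 to <40 |
| 8 | 4 | 16 | 16 to <40 |
| 10 | 5 | 20 | 20 to <40 |
| 20 | 10 | 40 | none |

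**Step 2: does the ≥40 limb do anything?** At LLOQ 10, a subject going from <10 to 40 has 40/5 = 8-fold, which already meets the 4-fold limb. The second limb therefore never adds a subject.

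**Step 3: which subjects change?** The literal rule was compared with a rule restricting the 4-fold limb to Day 0 ≥10, over all Day 0/Day 28 pairs on a two-fold scale (<10, 10, 20, …, 1280). At LLOQ 10 they differ in one cell only, <10 to 20. If half-step titers are reported, <10 to 28.3 differs as well. At LLOQ 20 they do not differ.

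**Step 4: size per subject.** 1/40 = 2.5 points, so 2, 4 or 6 affected subjects add 5, 10 or 15 points. For scale, assume 16/40 seroconvert under the restricted rule: 40% (Clopper-Pearson 95% CI 24.9% to 56.7%). Four affected subjects would make it 20/40: 50% (33.8% to 66.2%).

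**Step 5: MN, for comparison.** The MN limb runs from 7.1 to 28.3, and 28.3/7.1 = 3.99. If 7.1 is the value assigned to undetectable titers, the two limbs agree to rounding. If 7.1 were instead the MN LLOQ, the 4-fold limb would be met at 4 × 7.1/2 = 14.2, and the same gap would arise. The documents do not say which it is.

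**The case against.** The strongest reply is that the intended reading is plain. A reading that leaves half of a two-part definition with no work is unnatural, and a specific limb for undetectable baselines should govern over a general one. The MN rule points the same way, since its threshold is four times the undetectable value, just as 40 is four times 10. The derivation may also be fixed in the dataset specifications (SAP 1) or in study-specific laboratory documentation (Protocol 10.3.1), neither of which is available here. This is good evidence of intent, but it does not replace the written rule. Nothing in either document limits the 4-fold limb to measurable baselines.

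The second reply is that the overcount rests on an unstated LLOQ. That stands. The cut-off of 10 is described as a detection limit, and equating it with the LLOQ is an inference.

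The third reply is that the consequence is limited. That stands too. SAP 4.1 reports no sample size calculation, there is no SC success criterion, and Protocol 10.3.2 describes the comparisons with the active comparators as descriptive. SC is nevertheless tested across groups with Fisher's exact test under SAP 8.1, so p-values could move.

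A reader might go further and infer that the rule favours one arm. The documents do not support that: the rule is common to all arms, and no titer data are given. In a two-arm illustration starting from 16/40 in each, 8 affected subjects all in one arm give p = 0.117, and it takes 10 to reach p = 0.043. That pattern is extreme and assumed, and the SAP's own test is across all groups.

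**Conclusion.** The point holds as a conditional defect in a primary definition. At LLOQ 10, following the text literally counts rises from <10 to between 20 and <40 as SC, so an arm's rate can only rise or stay the same relative to the restricted rule. At LLOQ 20 nothing changes. The size is 2.5 points per affected subject in an arm of 40. The number affected is unknown and could be zero, because neither document gives baseline titers or expected fold rises. GMT and GMFR are unaffected, and so is the seroprotection rate as long as the LLOQ is at most 40.

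It would be tempting to conclude that reported SC rates are inflated, or that the first interim's formulation decision rested on inflated rates. The documents show neither the LLOQ nor how the flag was programmed, so neither inference is supported. That interim used data available as of the 12 February 2021 transfer, and a clarification to a March 2022 SAP cannot alter a decision taken on it.

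**What to change.** In SAP 8.1 and 8.2 and Protocol 10.3.2:

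- State the HI LLOQ for each strain and assay.
- Define HI SC as Day 0 <10 and post-vaccination titer ≥40, or Day 0 ≥10 and at least a 4-fold rise. Apply it at Days 28, 182 and 365 and to homologous and heterologous strains.
- State that an imputed half-LLOQ baseline may not satisfy the 4-fold limb when Day 0 is <10.
- State that, if an LLOQ exceeds 10, a baseline reported only as below the LLOQ requires a post-vaccination titer ≥40. Otherwise a baseline known only as <20 could not be assigned to either limb.
- Confirm that 7.1 is the value assigned to undetectable MN titers, so that the two MN limbs agree.

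If interim SC tables used the looser rule, record the change in SAP 11, which already notes a change to the SC testing ("Chi Square test were planned to compare number of subjects achieving SC and SP"), and show both versions. SAP 8 provides for listing all collected immunogenicity data, so both can be computed from the same titers.

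The cost is small. If the programmed flag already follows the restricted rule, only wording changes. If not, SC rates may be slightly lower, and the definition would be clarified after some sponsor staff had seen interim results (SAP 4.2.2 and 10). That is why both versions should then be reported.

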10.3.2 Immunogenicity Endpoints

Unless otherwise mentioned, point estimates and 95 % CI will be calculated for all immunogenicity endpoints and responses in the adjuvanted QVLP recipients will be compared with the active comparator groups using descriptive statistics.

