12.6 Immunogenicity Analyses

12.6.1 Analysis of Primary Endpoint

The primary immunogenicity endpoint is defined in Section 10.3.2.1.

The following analyses for the HI assay (homologous strains) will be performed on the PP set:

- GMT (Day 0 and Day 28): The point estimates and the corresponding two-sided 95 % CI by treatment group and strain will be calculated as the antilog of the mean and 95 % CI of log transformed titer values;
- SC rate (Day 28): The point estimates and the corresponding two-sided 95 % CI for subjects achieving SC by treatment group and strain will be calculated and reported;
- SP rate (Day 0 and Day 28): The point estimates and the corresponding two-sided 95 % CI for subjects achieving SP by treatment group and strain will be calculated and reported;
- GMFR: the geometric mean of the ratio of GMTs (Day 28/Day 0).

The GMFR will be derived by using ANCOVA to model the difference in the log of the titer values between Day 28 and Day 0, with treatment group as main effect and baseline titer as covariate.

GMT for HI will be compared between treatment groups using the analysis of variance (ANOVA) model. GMFR for HI will be compared using the ANCOVA model. For SC rate and SP rate, Fisher's exact tests or chi square tests will be used to compare between the treatment groups.

Analyses of primary immunogenicity endpoint will include each group as a whole.

The analyses of the primary immunogenicity endpoints will also be performed using the ITT set.

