# **Immunogenicity:**

The primary immunogenicity endpoint is:

HI antibody response induced by adjuvanted and unadjuvanted QVLP and Fluzone HD Quad against the homologous influenza strains on Day 28, compared to Day 0 values. HI antibody titers will be analyzed using the following parameters: geometric mean titers (GMT), seroconversion (SC) rate, seroprotection (SP) rate, and geometric mean fold rise (GMFR).

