The statistical analysis method of secondary immunogenicity endpoints is the same as the primary endpoint analysis for the relevant parameters, including GMT, SC rate, SP rate and GMFR.

SAS code is presented in Appendix 13.3.

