# 13.3. SAS code for Immunogenicity Analyses

# To calculate adjusted GMT and do the ANOVA:

PROC MIXED data=tab(where=(avisitn = Day <0, 28, 182, 365>)); \*\* to be repeated for each relevant timepoints

BY STRAIN;

CLASS TRT:

MODEL var = TRT; \*\* where var=LOG10(Analysis value)

LSMEANS TRT / DIFF=ALL CL ALPHA=0.05 ADJUST=tukey;

RUN:

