# To calculate adjusted GMFR and do the ANCOVA:

PROC MIXED data=tab(where=(avisitn = Day <0, 28, 182, 365>)); \*\* to be repeated for each relevant timepoints

BY STRAIN;

CLASS TRT:

MODEL var = TRT BASE; \*\* where var=LOG10(Analysis value/Baseline value) and BASE is LOG10(Baseline value)

LSMEANS TRT / DIFF=ALL CL ALPHA=0.05 ADJUST=tukey;

RUN;

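### The code headed as giving adjusted GMTs has treatment as its only term, so post-vaccination GMTs are compared without the Day 0 titer, while the GMFR ANCOVA tests the same contrast with it

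*SAP*

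**What the plan says.** The primary immunogenicity endpoint (SAP 3.2.1) is the Day 28 HI response against homologous strains. There "HI antibody titers will be analyzed using the following parameters": GMT, seroconversion rate, seroprotection rate and GMFR, listed side by side without rank.

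- **GMT.** SAP 8.1 compares log GMTs "by using the analysis of variance (ANOVA) model on log-transformed titer values", with Tukey's test for pairs. Protocol 12.6.1 agrees: "GMT for HI will be compared between treatment groups using the analysis of variance (ANOVA) model". The code block in SAP 13.3 is headed "To calculate adjusted GMT and do the ANOVA", but treatment is the only term in its model statement.
- **GMFR.** SAP 8.1 compares GMFRs by ANCOVA "with treatment group as main effect and baseline as covariate on log-transformed titer values fold rise from pre-vaccination". The code is "MODEL var = TRT BASE", with log10(post/baseline) as response and log10 baseline as covariate.
- **GMFR estimate.** SAP 8.1 calculates GMFR and its CI from the raw mean log ratio. Protocol 12.6.1 derives GMFR from the ANCOVA, and the second code block in SAP 13.3 is headed as giving an adjusted GMFR.
- **Secondary endpoints.** SAP 8.2: "The statistical analysis method of secondary immunogenicity endpoints is the same as the primary endpoint analysis for the relevant parameters". The same pair of tests therefore recurs there.
- **Precedence.** SAP 4.4 and protocol 12.1.3 put the PP set ahead of the ITT set. No passage ranks the GMT comparison against the GMFR comparison.

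**The concern.** The Day 0 titer is collected and is already a covariate for GMFR, yet it is left out of the GMT comparison. If baseline and Day 28 log titers are correlated, that gives up precision at no saving, in a trial of 40 per arm with no sample size calculation (SAP 4.1).

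The two comparisons also look like evidence on different parameters, although under randomization they target the same Day 28 GMT ratio. For a given strain and pair of arms, a reader may meet two estimates and two Tukey p-values, one significant and one not, with no guidance on which to use. The word *adjusted* sits on the output that adjusts for nothing. Both parameters feed the first interim analysis, which informs the choice of formulation for a later study (SAP 10).

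**Working it through.** **Inputs from the documents.** 40 per arm in three arms (SAP 4.1); two-sided alpha 0.05 with Tukey adjustment (SAP 13.3); five stopped arms included in the analyses like the other groups (SAP 4), making eight groups. There is no planned power, SD or effect size to reproduce.

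**Assumed.** Log10 titer SD 0.5, equal at Day 0 and Day 28; within-arm correlation rho from 0 to 0.7; true GMT ratio 1.5 or 2.0 for one arm.

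**1. What the GMT code produces.** With one classification factor and no covariate, the least-squares means are the raw group means of log titer. Nothing is adjusted.

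**2. The two contrasts.** Let Y be log post-vaccination titer and B log baseline. The GMFR model is

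Y − B = μ + τ + γB + e, which is the same as Y = μ + τ + (1 + γ)B + e.

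Treatment effects τ, residuals and standard errors are identical; only the slope shifts by 1. On one simulated data set (3 × 40, SD 0.6, rho 0.5):

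| Model | Difference | SE | p (not Tukey-adjusted) | Baseline slope |
|---|---|---|---|---|
| ANCOVA, log fold rise | 0.280249 | 0.107402 | 0.0103 | −0.574222 |
| ANCOVA, log Day 28 titer | 0.280249 | 0.107402 | 0.0103 | 0.425778 |
| ANOVA, log Day 28 titer | 0.321448 | 0.119213 | 0.0080 | none |

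The slopes differ by 0.425778 + 0.574222 = 1. The ANOVA estimate differs by 0.321448 − 0.280249 = 0.041199, which is the slope times the chance baseline difference between the arms. Here that imbalance gave the ANOVA the smaller p-value despite its larger SE.

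**3. Precision.** SE(ANOVA) = SD × √(2/n) = 0.5 × √(2/40) = 0.112. SE(ANCOVA) ≈ SE(ANOVA) × √(1 − rho²), so the relative gain in interval width is 1 − √(1 − rho²) and does not depend on the SD.

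| rho | Closed form | Simulated median |
|---|---|---|
| 0 | 0% | −0.4% |
| 0.2 | 1 − √0.96 = 2.0% | 1.3% |
| 0.3 | 1 − √0.91 = 4.6% | 4% |
| 0.4 | 8.3% | 7.6% |
| 0.55 | 16.5% | 15.9% |
| 0.7 | 28.6% | 28.1% |

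With two-fold dilution titers and values below 10 set to 5 (assumed Day 0 GMT 25 and four-fold rise), the reduction is 6.7% at rho 0.4 and 24.8% at 0.7.

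**4. Disagreement, three arms of 40.** Tukey critical value 2.374; 20,000 simulated trials per cell; entries are for rho 0.4 / 0.55 / 0.7.

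| True ratio | One significant, other not | ANCOVA only | ANOVA only | ANOVA rejects | ANCOVA rejects |
|---|---|---|---|---|---|
| 1.5 | 10.6 / 16.8 / 28.2% | 7.2 / 13.3 / 24.7% | 3.3 / 3.5 / 3.6% | 21.7 / 21.2 / 21.6% | 25.5 / 31.0 / 42.7% |
| 2.0 | 13.8 / 21.3 / 30.6% | 11.0 / 19.0 / 29.7% | 2.8 / 2.3 / 0.9% | 62.4 / 63.4 / 62.4% | 70.6 / 80.2 / 91.3% |

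With no true effect, 1.4 / 2.3 / 2.8% disagree. At SD 0.4 and 0.6 the range for ratios 1.5-2.0 is 8.6-36.0%. At rho 0-0.3 disagreement is 2-10%. Significant results in opposite directions did not occur in 540,000 trials.

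**5. Disagreement, eight groups.** Sizes of the stopped arms are not given; 10 to 25 each is assumed (6,000 trials, SD 0.5, rho 0.4-0.7). The critical value rises to about 3.06-3.07. ANOVA rejection falls to about 7-8% at ratio 1.5 and 35-38% at ratio 2.0. Disagreement is about 5-16% and 14-42% respectively.

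**The case against.** **No analysis is missing or invalid.** The baseline-adjusted contrast is prespecified under GMFR, no margin or success criterion depends on either test, and protocol 10.3.2 says "responses in the adjuvanted QVLP recipients will be compared with the active comparator groups using descriptive statistics", unless otherwise mentioned. This stands as a limit on severity. It does not remove the point, because Tukey p-values are planned for both comparisons (protocol synopsis, Statistical Methods; SAP 8.1 and 13.3).

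**The ANOVA is coherent.** It tests exactly the raw GMTs that are displayed, and protocol and SAP agree on it; an adjusted ratio will not equal the ratio of the displayed GMTs. True, and a reason to keep the ANOVA as a labelled supportive analysis.

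**The gain rests on assumptions.** It does. At zero correlation there is none, and the disagreement rates also depend on how many arms enter the model.

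**Ranking GMT against GMFR does not rank all four parameters.** Correct. But these two are the same contrast with and without a covariate, which cannot be said of the seroconversion and seroprotection rates.

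**A change after unblinded interims invites suspicion.** This is a fair caution. It is eased because the contrast is already prespecified for GMFR and the planned ANOVA would still be shown.

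**Stronger readings to avoid.** A reader might infer that the GMT comparison is biased, or that the two tests could support opposite conclusions about which vaccine is better. Randomization makes both tests valid, and the simulations show one test missing an effect, not a reversal of direction. Nor do the documents tie any pass/fail decision to either p-value.

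**Conclusion.** The point holds as a matter of precision and clarity, worth correcting but not critical. Certain from the text: the GMT code block is mislabelled, the GMT comparison omits the Day 0 titer, the GMFR ANCOVA tests the same treatment contrast with it, and the documents do not agree on whether the displayed GMFR is raw or ANCOVA-derived.

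The size is conditional. The interval gain of about 8-28% needs a correlation of 0.4-0.7 and fades to nothing at 0. The disagreement rates additionally depend on the assumed SD and true ratio, and on whether three or eight groups are modelled. They illustrate the problem and do not predict this trial. In the three-arm results, most disagreement is the ANOVA missing an effect that the ANCOVA detects.

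**What to change.** In SAP 8.1, 8.2 and 13.3 and protocol 12.6:

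- Compare GMTs at Days 28, 182 and 365 (Day 28 only for MN), not at Day 0, using "MODEL var = TRT BASE" with log10 titer as response and log10 baseline titer as BASE.
- Report this contrast once, as the baseline-adjusted GMT ratio with 95% CI, and state that it equals the GMFR ANCOVA contrast.
- Keep raw GMTs (including Day 0) and the treatment-only ANOVA as supportive, labelled unadjusted.
- State which GMFR is displayed, raw or ANCOVA-derived, and label each one shown.
- Report the number of ITT subjects without a Day 0 titer.
- Record that the change was made on design grounds after the planned unblinded interims.

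**Cost.** Wording in both documents, a protocol amendment and one degree of freedom; no new data. ITT subjects without a Day 0 titer drop out of the adjusted model but stay in the supportive ANOVA. The post-vaccination PP sets already require a Day 0 assessment. If the models are left alone, the minimum is to correct the code heading, say that the GMFR ANCOVA is the baseline-adjusted comparison and leads, and label the displayed GMFR.
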